### **Preliminary Data:**

**Aerobic exercise enhances indices of neuroplastic potential.** Single sessions of AEx can enhance neuroplastic potential and serum BDNF suggesting that it may ‘prime’ the brain for a subsequent rehabilitation intervention. Work from our lab indicates that, in neurologically intact subjects, AEx increases neuroplastic potential (Figure 1.a) and serum BDNF in an intensity dependent manner. Currently, we have an ongoing project investigating the acute effect of AEx on neuroplastic potential in chronic stroke survivors (Fig 1.b).

**Exploring a bout of priming AEx that fits into current clinical model.** Current AEx priming models in UE stroke rehabilitation have incorporated priming bouts that have exceeded 30 minutes. This could be problematic for stroke survivors lacking endurance to complete a 30-minute bout of AEx before rehabilitation. Additionally, extended priming bouts may be clinically burdensome if resources or staff is limited or if it incurs greater cost to the stroke survivor. Thus we are seeking to find a potent, yet time efficient, priming bout of AEx. Our previous work indicates that 15 minutes of AEx was sufficient in enhancing neuroplastic potential (Figures 1.a and 1.b) for up to 60 minutes post-AEx.

[figure not shown]

Figure 1. The acute effects of AEx on neuroplastic potential in control subjects (1a, n=38) and stroke subject (1b, n=1). Note that AEx (red and blue lines) enhances neuroplastic potential compared to sitting (black line).

### 3.0 Intervention to be studied

This project involves the study of the effects of the combination of AEx and an UE motor practice intervention (DDP) on UE function in chronic stroke survivors. A preceding 15-minute bout of AEx will serve as a ‘primer’ to enhance the effects of the DDP intervention on UE function. Duck Duck Punch (DDP) is an interactive game with an old time carnival theme. In 2015 DDP received FDA clearance for use as a rehabilitation device for post-stroke upper extremity rehabilitation. The patient sits (we prioritized safety so that the player sits vs. stands) in front of the Microsoft Kinect and controls a virtual arm with his/her physical arm; reaching forward to “punch” virtual ducks (Figure 2). The game can be customized, i.e., made easier or harder, so that patients with all levels of impairment can play. Success motivates continued play, so that the user engages in high-repetition UE movement practice. Importantly, DDP was deliberately designed by therapists so that all aspects of the game elicit beneficial therapeutic arm and postural movements. These beneficial movements are ensured via:

**Trunk Constraint:** Trunk motions will be constrained by fixing the shoulder avatar in space meaning that the avatar arm does not respond to attempts to use compensatory trunk motion to “punch” the target rather than reach forward with the arm. As shown in the photos, the avatar hand moves forward only when the patient reaches forward using shoulder flexion-elbow extension not when he/she leans the trunk forward. Therefore, when a therapeutically beneficial (i.e., “therapist approved”) strategy is used, the patient experiences the reward of successful game play to reinforce the movement strategy.

**Avatar Elbow Extension Scaling:** During set-up, the Kinect maps the patient’s actual hemiparetic arm movement abilities and displays it on the screen. The user (therapist or patient) can scale, i.e., exaggerate, the patient’s actual arm motion so that the avatar arm has more movement than the hemiparetic arm. This enables patients who have limited range of motion in the real-world, to have full range of motion in the virtual world which allows them to successfully play the games. The importance of this feature is that it enables the difficulty of game play sessions to match the patients’ levels of ability. A task-difficulty to patient-ability match is required to facilitate post-stroke motor skill (re)learning that underlies recovery. If game play is too difficult, i.e., if the patient does not have enough skill to achieve the task goal, compensatory trunk and/or arm movement strategies will be used. Atypical, poor quality motions (learned bad-use) may inhibit overall recovery. Matching

Figure 2. A subject playing Duck Duck Punch

game difficulty to players' ability allows a combination of both errors and success during repetitive practice thereby providing implicit and explicit feedback to challenge the nervous system and promote learning of good quality motions.

## 4.0 Inclusion and Exclusion Criteria/ Study Population

**Eligibility screening:** Subjects (male and female), ages 21-90, will be screened and recruited for the study six months to ten years post-stroke, allowing for natural recovery during the first 6 months post-stroke. The pool of candidates for the study will be recruited from the database registry supported by the Clinical and Translation Tools and Resources (CTTR) Core of the NIH-funded Center of Biomedical Research Excellence (COBRE) in Stroke Recovery at MUSC.. Eligible participants will be screened for participation and if appropriate will be accepted into the study.

**Inclusion criteria:** 1) experienced unilateral stroke at least 6 months, but no more than 120 months prior; 2) voluntary shoulder flexion of the affected arm  $\geq 20^\circ$  with simultaneous elbow extension  $\geq 10^\circ$ ; 3) moderate arm movement impairment (UE Fugl-Meyer Assessment  $> 21$  but  $< 52$  points; 4) passive range of motion in paretic shoulder, elbow, wrist, thumb and fingers within 20 degrees of normal; 5) 21-90 years of age; 6) ability to communicate as per the therapists' judgement at baseline testing; 7) ability to complete and pass an exercise tolerance test.

**Exclusion criteria:** 1) lesion in brainstem/cerebellum as these may interfere with visual-perceptual/cognitive skills needed for motor re-learning; 2) presence of other neurological disease that may impair motor learning skills; 3) orthopedic condition or impaired corrected vision that alters reaching ability (e.g., prior rotator cuff tear without full recovery); 4) paretic arm pain that interferes with reaching; 5) unable to understand or follow 3-step directions; 6) severe cognitive impairment (Montreal Cognitive Assessment score  $< 22$ ); 7) severe aphasia; 8) inability to read English, 9) history of congestive heart failure, unstable cardiac arrhythmias, hypertrophic cardiomyopathy, severe aortic stenosis, angina or dyspnea at rest or during ADL's; 10) Severe hypertension with systolic  $> 200$  mmHg and diastolic  $> 110$  mmHg at rest; 11) history of, or current, depression; **and for brain stimulation procedures only:** 12) women of child-bearing potential; 13) electronic or metallic implants; 14) history of seizures.

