**Exercise Tolerance Testing:** Prior to experimental visits, a bicycle ergometry protocol modified from the LEAPS trial will be used to assess exercise tolerance prior to study inclusion. The protocol will be overseen by a physician and will commence with the subject seated quietly for two minutes. Exercise will begin with the subject pedaling at ~60 revolutions per minute (RPM) and 0 Watts (W) of workload, with workload will be increased by ~15 W every 3 minutes. If the pedal cadence drops below 50 RPM, additional reminders will be given. Testing continues until maximal effort is achieved. The test will be terminated prior to achieving maximum effort for predefined symptomatic, clinical, and electrocardiographic criteria. Symptom-related reasons for termination include angina, dyspnea, and fatigue. Fatigue is defined as either voluntary exhaustion or inability to maintain a minimum cycling cadence of 40 RPM. Clinical criteria for termination include: 1) Hypertension:  $\geq 220/120$  mmHg, or 2) Hypotension: a drop in diastolic blood pressure  $>20$  mmHg, and O2 saturation  $<85\%$ . Electrocardiogram criteria include: 1)  $\geq 1$  mm horizontal or down sloping ST segment depression, 2) sustained paroxysmal ventricular tachycardia ( $>30$  beats), and 3) sustained paroxysmal supraventricular tachycardia ( $>30$  beats). If the test is terminated because of electrocardiographic findings, the subject will be managed medically as needed, referred for care, and disapproved for participation. Resting blood pressure and heart rate will be obtained prior to initiation of exercise as well as after the subject has been sitting on the stationary bicycle for 1 minute. During the exercise test, blood pressure readings will be obtained every 3 minutes. Heart rate will be obtained from the 12-lead EKG. Maximal heart rate will be recorded as the highest heart rate achieved during the exercise tolerance test.

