### 13.0 Risks to Subjects

**Screening:** This activity will involve answering a few questions that could cause the participant to become upset, emotionally distressed, or embarrassed. To reduce this risk, screening will occur in a private office with only study personnel present.

**NeuroCom Balance Master™ Test:** The participant will wear a safety harness attached to the top of the machine so that a fall cannot occur (weight limit 500 lbs), and a research assistant will be in close proximity to provide assistance if a loss of balance does occur. If a participant is unable to complete conditions due to loss of balance or dizziness, the assessment will be stopped.

**Aerobic Exercise:** The risks of exercising at submaximal intensities on a cycle ergometer (as proposed in this study) are minimal but could include fainting, abnormal blood pressure response, irregular heartbeat, dizziness, and muscle soreness. However to ensure safety, all participants will complete an exercise tolerance test evaluated by a physician. The risk of serious adverse response to exercise testing, which is a greater intensity than will be prescribed in this study, has been reported to be less than 1 in 2500 cases. Study personnel will monitor participants' vital signs (heart rate and blood pressure) before, during, and after exercise. Given the low likelihood of an adverse response to submaximal exercise and screening prior to participation we believe the risk of exercise to be low. In addition, professional staff (exercise physiologist, physical therapist) will be present and available throughout each session.

**Duck Duck Punch:** The treatment session duration and number of movement repetitions (200/session) may induce fatigue or pain, primarily in the paretic arm. Subjects in [name] DDP studies have averaged ~200 repetitions per session and empirical evidence suggests that chronic stroke survivors can safely achieve 200-300 arm movement repetitions per in a 1-2 hour therapy session. To assess and monitor pain and fatigue, subjects will be instructed in how to use the Borg Rating of Perceived Exertion scale and a 10-point Pain Rating Scale.

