### **Protection against risks**

An exercise physiologist, occupational therapist, or physical therapist will be present during all testing and intervention sessions and a nurse will perform all blood draws. All participants will be screened prior to participating in exercise or brain stimulation procedures to ensure safety. Any adverse events will be recorded and monitored as required by our Institutional Review Board. The PI on this proposal is an exercise physiologist, a certified strength and conditioning specialist and has approximately 10 years experience in the development and implementation of exercise interventions and three years experience delivering TMS. In the event of an adverse medical event, standard facility emergency procedures will be followed and proper personnel notified. Any adverse events will be recorded and monitored as required by the IRB. Subjects will be able to terminate the training or testing sessions at their request at any time without prejudice.

**Aerobic exercise:** During all exercise sessions the research staff will closely monitor the subject to ensure their comfort. Minimization of risk will be accomplished by monitoring vital signs within prescribed criteria for termination of aerobic exercise. We will follow the American College of Sports Medicine criteria for terminating an exercise session, which includes: subject complaints of light-headedness, confusion, or dyspnea; onset of angina; excessive blood pressure changes (systolic BP greater than 220 mmHg, diastolic BP greater than 110 mmHg); and inappropriate bradycardia (drop in heart rate >10 beats per minute).

**Duck Duck Punch:** We will document subjects' perceived exertion and pain before, during and after each therapy session in a written log. Ratings of 12-14 on the Borg scale (6-20) suggest that the activity is being performed at a moderate intensity level. If a Borg rating  $\geq 14$ , or if a pain rating  $\geq 5$  (moderate; 0-10 scale), then subjects will rest and we will reduce DDP game difficulty. Subjects' ratings will be reviewed by study personnel and adjustments to the individual subject's program will be made as needed.

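### Exclusion 10 joins its two resting blood pressure limits with 'and', so read literally it admits someone resting at 190/115 to a maximal-effort test; change it to 'or' (minor: Section 13.0 conflicts with 4.0 and 9.0 on TMS contraindications)

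*Combined protocol and SAP*

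**What the plan says.** Three blood pressure rules matter here.

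- **Entry (Section 4.0, exclusion 10):** "Severe hypertension with systolic $> 200$ mmHg and diastolic $> 110$ mmHg at rest".
- **Exercise tolerance test (Section 9.0):** "Testing continues until maximal effort is achieved", unless a stop rule applies. The blood pressure stop rule reads: "Clinical criteria for termination include: 1) Hypertension: $\geq 220/120$ mmHg".
- **Training sessions (Section 13.0, Protection against risks, Aerobic exercise):** the session ends for excessive pressure changes, given as "systolic BP greater than 220 mmHg, diastolic BP greater than 110 mmHg".

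The plan has other safeguards. Inclusion 7 requires "ability to complete and pass an exercise tolerance test". Section 9.0 has a physician oversee the test and states that "Resting blood pressure and heart rate will be obtained prior to initiation of exercise". Section 13.0 adds that "all participants will complete an exercise tolerance test evaluated by a physician". Section 9.0 spells out disapproval for one kind of termination only: "If the test is terminated because of electrocardiographic findings, the subject will be managed medically as needed, referred for care, and disapproved for participation".

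On TMS, Section 4.0 applies exclusions 12 to 14 to brain stimulation procedures alone, and the TMS screen in Section 9.0 bars people with a contraindication from the TMS assessments alone. The TMS paragraph of Section 13.0 instead bars people with absolute contraindications from the whole study and makes passing the TMS screen a condition for every participant.

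**The concern.** A resting-pressure exclusion should act before the person is exposed to exercise. Joined by 'and', exclusion 10 acts only when both components are high, so isolated severe diastolic or isolated severe systolic hypertension passes it. The next step is the hardest exercise in the study: Section 13.0 itself describes exercise testing as more intense than the prescribed sessions. On a literal reading, a person whose resting diastolic would end a submaximal session may still start the maximal test.

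No other numerical resting limit stands in the way. Section 9.0 takes a resting reading but gives no value that prevents the test from starting, and nothing says what passing means in terms of blood pressure. What is at stake is an avoidable risk at the test, or a visit stopped once pressure is read, since it is also taken at the baseline of every training session.

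The TMS conflict is separate and smaller. Two screeners following different sections could reach opposite enrolment decisions for a person with, say, a metal implant.

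**Working it through.** No sample size, power or error rate depends on this point. The check is one of logic.

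**Inputs** (S = systolic, D = diastolic, whole mmHg)

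- Exclusion 10 as written (Section 4.0): S > 200 *and* D > 110.
- Exclusion 10 as proposed: S > 200 *or* D > 110.
- Session stop (Section 13.0): limits of S > 220 and D > 110, separated only by a comma. Read separately: S > 220 or D > 110.
- Test stop (Section 9.0): 220/120. Read separately: S ≥ 220 or D ≥ 120.

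**Individual resting readings, session and test limits read separately**

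| Reading | Exclusion 10 as written | Exclusion 10 with 'or' | Session stop | Test stop |
|---|---|---|---|---|
| 190/115 | not excluded | excluded | met | not met |
| 180/119 | not excluded | excluded | met | not met |
| 210/100 | not excluded | excluded | not met | not met |
| 240/105 | not excluded | excluded | met | met |
| 190/125 | not excluded | excluded | met | met |
| 201/111 | excluded | excluded | met | not met |
| 200/110 | not excluded | not excluded | not met | not met |

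For 190/115: 190 > 200 is false, so the conjunction fails although 115 > 110 is true.

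**The gap against the session rule.** This is the set of readings that exclusion 10 lets through, that would end a session, and that do not already meet the test stop.

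1. Not at the test stop: S < 220 and D < 120.
2. Would end a session: with S < 220, this requires D > 110, so D is 111–119.
3. Not excluded as written: with D > 110, this requires S ≤ 200.

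The result is D 111–119 with S ≤ 200. The diastolic margin to the test stop runs from 120 − 111 = 9 mmHg to 120 − 119 = 1 mmHg. At 190/115 the margins are 120 − 115 = 5 mmHg diastolic and 220 − 190 = 30 mmHg systolic.

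**The mismatch with exclusion 10's own limits.** One component is above 200 or 110, the person is not excluded, and the test stop is not met. This gives the range above plus a second one: S 201–219 with D ≤ 110. That second range breaches exclusion 10's systolic figure but not the session limit of 220.

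**Sensitivity to how the other rules are read**

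- Session limits separate, test limits needed jointly: the session-rule gap widens. For example, 225/105 now falls in it.
- Session limits needed jointly (S > 220 and D > 110): the gap is empty under either reading of the test stop, because such a person already exceeds both entry limits. The own-limit mismatch remains.
- Exclusion 10 with 'or': anyone admitted has S ≤ 200 and D ≤ 110, so the session-rule gap and the own-limit mismatch are both empty under all four combinations of session and test readings.

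**TMS wording side by side.** Section 4.0 (exclusions 12–14) and Section 9.0 (TMS screen) withhold TMS only. Section 12.0 describes the screening tool as being for those who undergo TMS. Section 13.0 alone withholds the study. Under both versions nobody with an identified contraindication receives TMS; only enrolment differs.

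**The case against.** The strongest reply is that 'and' here simply lists two limits, each of which defines severe hypertension. Section 9.0 does something similar when it joins a diastolic fall of more than 20 mmHg and oxygen saturation below 85% with 'and', although staff would hardly wait for both before stopping. This is plausible. But if 'or' was meant, the edit only states the intention, so the argument favours the change.

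A second reply is that the comparison with the session rule reads exclusion 10 strictly and the session rule loosely. That is fair as far as it goes: if both session limits must be exceeded, the gap against that rule vanishes. The session rule is also a stop rule for a different activity, so differing numbers do not by themselves prove an error. The literal failure of exclusion 10 on its own limits does not depend on that comparison.

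A third reply is that the risk is largely handled elsewhere. A physician oversees and evaluates the test. Pressure is read at rest, again after a minute on the bicycle, and every 3 minutes during the test. Inclusion 7 demands a pass, and every session begins with a reading. This mitigation is real and limits the weight of the point. It does not supply a written cut-off before the test, and passing the test comes after exposure to it.

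On TMS, the eligibility, screening and monitoring sections agree and only the risk section is out of step. That is why the point is minor.

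**Conclusion.** The concern holds. As written, exclusion 10 does not exclude resting pressures such as 190/115 or 210/100 before a maximal-effort test, and no other numerical resting limit is stated. With session and test limits read separately, the gap against the session rule is diastolic 111–119 with systolic at or below 200. Systolic 201–219 with diastolic at or below 110 is a second mismatch, with exclusion 10's own limit only.

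This rests on a literal reading of 'and', which may be loose drafting. The session-rule comparison also assumes that the session limits apply separately. The check shows that a gap exists, not how often anyone would fall into it; the documents give no frequency. No undetected harm is claimed, and no analysis or decision threshold changes. It is a safety-relevant eligibility wording that should be corrected, with partial safeguards already in place.

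The TMS inconsistency is real but minor. It affects only who may enrol, although one person is 1/10 = 10% of the planned sample.

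**What to change.** **Main.** In exclusion 10, replace 'and' with 'or', so that resting systolic above 200 mmHg or resting diastolic above 110 mmHg excludes, and have the study physician confirm it. No new pressure value is needed. The cost is a wording amendment with no added procedure; slightly fewer people may be eligible.

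**Minor.** In the TMS paragraph of Section 13.0, exclude people with absolute contraindications from TMS procedures instead of from the study, and limit the TMS-screen requirement to those undergoing TMS, as Section 12.0 already does. People with contraindications then stay eligible for the intervention, so the PAS and corticomotor excitability measures may have fewer than 10 participants. Both edits can go into one amendment.

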## 5.0 Number of Subjects

A total of 10 chronic stroke survivors will be accrued locally.

## 6.0 Setting

All study procedures will take place at MUSC.

**Functional Neurostimulation Laboratory (FNL):** This laboratory provides state-of-the-art brain stimulation resources to support research activities. The bulk of research procedures for this proposal will take place in this laboratory. The FNL is physically located in the College of Health Professions Research building although researchers from various disciplines, including neurology, psychiatry, and rehabilitation, regularly collaborate in this lab. This lab offers state-of-the-art brain stimulation equipment that can be utilized for a multitude of research protocols. The primary brain stimulation tools are a MagStim BiStim^2 and MagStim Rapid transcranial magnetic stimulator modules (The Magstim Company Limited; Whitland, UK). The stimulators can be outfitted with a figure-of-eight, double-cone, or air-cooled coil. The combination of these brain stimulation tools allow researchers to perform a variety of protocols including single pulse, paired pulse, and repetitive pulse to assess either upper or lower extremity neurophysiology. The lab is also equipped

with a stereotaxic passive marker and camera system as well as neuro-navigation software. Magnetic resonance images can be uploaded to the neuro-navigation software, which allows researchers to identify and accurately stimulate brain structures of interest. Neurophysiological data is collected using a multi-channel data acquisition and analysis package consisting of Spike2 v7.12 software (Cambridge Electronic Design; Cambridge, UK), a CED 1902 amplifier (Cambridge Electronic Design; Cambridge, UK), and a CED Micro 1401-3 data acquisition unit (Cambridge Electronic Design; Cambridge, UK). Additionally, the lab is equipped with a constant current stimulator and train/delay generator for paired peripheral nerve and brain stimulation protocols (i.e. paired associative stimulation). The myriad of tools available in this lab allows researchers to perform and analyze mostly all brain stimulation protocols. Specific to this proposal, there is ample space to perform the aerobic exercise protocol within the laboratory. Additionally there is a laboratory space adjacent to the FNL, which provides ample space for pre-participation screening. This reduces travel time between laboratories, and provides convenience for both study personnel and participants.

**Upper Extremity Motor Function Laboratory:** This MUSC supported laboratory features resources directed to generating and implementing innovative and scientifically-based rehabilitation interventions to improve recovery of UE motor function after neurological injury/disease. This lab features a virtual environment (enabling DDP intervention) and a multitude of assessment tools used in UE rehabilitation trials.

**Locomotor Rehabilitation Laboratory:** This 800 ft laboratory is a shared resource supported in part by the Department of Health Sciences and Research, and features equipment capable of collecting kinematic, and electromyographic data during walking. Additionally, a COSMED Quark Cardio-Pulmonary Exercise Metabolic Analyzer is housed in this lab and provides the ability to assess respiratory gas exchange and electrocardiographic activity during exercise. Various exercise equipment (3 recumbent bikes, 2 treadmills, 1 recumbent step trainer) with appropriate safety apparatuses (overhead support system) are available in this lab.

